### **3.3.3 Objective Response Rate**

The ORR is defined for the SAF as follows:

- The ORR is the proportion (%) of patients with an overall response of CR or PR (confirmed by a follow-up scan at least 4 weeks after showing CR or PR).

A confirmed response of CR/PR means that a response of CR/PR is recorded at one visit and confirmed by repeat imaging, preferably at the next regularly scheduled imaging visit, and not less than four weeks after the visit when the response was first observed, with no evidence of progression between the initial and CR/PR confirmation visit. Both visits contributing to the confirmed response must be prior to any subsequent anti-cancer therapy for the patient to be

considered as a responder.

Data obtained up until progression, or the last evaluable assessment in the absence of progression, will be included in the assessment of the ORR. Responses that occur after the start of subsequent anti-cancer therapy must be excluded from the derivation of ORR (ie, only responses that occur prior to receiving subsequent therapy will be included in the numerator).

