- (a) Patients with measurable disease and/or nonmeasurable and/or no evidence of disease assessed at baseline by computed tomography (CT)/magnetic resonance imaging (MRI) will be eligible for this study.
- (b) Prior irradiated lesions may be considered measurable and selected as target lesions (TLs) providing they fulfill the other criteria for measurability.

10 WHO/ECOG PS of \leq 2.

11 No prior exposure to immune-mediated therapy including, but not limited to, anti-CTLA-4, anti-PD-1, anti-PD-L1, and antiprogrammed cell death ligand 2 (anti-PD-L2) antibodies, excluding therapeutic anticancer vaccines.

12 Adequate organ and marrow function as defined below:

- Hemoglobin \geq 9.0 g/dL
- Absolute neutrophil count \geq 1.0×10^9 /L
- Platelet count \geq 75×10^9 /L
- Serum bilirubin \leq 1.5 \times the upper limit of normal (ULN). This will not apply to patients with confirmed Gilbert's syndrome, who will be allowed in consultation with their physician.

- Alanine aminotransferase (ALT) and aspartate aminotransferase (AST) $\leq 2.5 \times$ ULN
- Measured creatinine clearance (CL) > 30 mL/min or calculated CL > 30 mL/min as determined by Cockcroft-Gault (using actual body weight).

Males:

$$\text{Creatinine CL} = \frac{\text{Weight (kg)} \times (140 - \text{Age})}{72 \times \text{serum creatinine (mg/dL)}}$$

Females:

$$\text{Creatinine CL} = \frac{\text{Weight (kg)} \times (140 - \text{Age})}{72 \times \text{serum creatinine (mg/dL)}} \times 0.85$$

13 Must have a life expectancy of at least 12 weeks.

Weight

14 Body weight > 30 kg at enrollment and first IP dose administration

Sex

15 Male or female

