9.3 Definitions of analysis sets

All analyses will be performed on the safety analysis set.

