#### 2.1.1 Safety Analysis Set

The Safety Analysis Set: will consist of all patients who received at least one dose (partial or in full) of durvalumab. The SAF will be used for analysis of all safety endpoints. In this safety study, the standard full analysis set will be same as SAF, therefore, the SAF will be used for analysis of efficacy endpoints as well.

For analysis of time-to-event endpoints, the SAF will be used with defined censored patients.

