**Table 4 Overall Visit Responses**

Target	Non-target	New Lesions	Overall Visit Response
CR	CR (or NA)	No (or NE)	CR
CR	Non-CR/Non-PD or NE	No (or NE)	PR
PR	Non-PD or NE or NA	No (or NE)	PR
SD	Non-PD or NE or NA	No (or NE)	SD
PD	Any	Any	PD
Any	PD	Any	PD
Any	Any	Yes	PD
NE	Non-PD or NE or NA	No (or NE)	NE
NA	CR	No (or NE)	CR
NA	Non-CR/Non-PD	No (or NE)	SD
NA	NE	No (or NE)	NE
NA	NA	No (or NE)	NED

CR complete response; PR partial response; SD stable disease; PD progression of disease; NE not evaluable; NA not applicable (only relevant if there were neither target nor non-target lesions at baseline); NED no evidence of disease.

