### **3.3.4 Best Objective Response**

Best objective response (BoR) is the best response a patient has had after Day 1 up until progression, or the last evaluable assessment in the absence of progression. Responses that occur after the start of subsequent anti-cancer therapy must be excluded from the derivation. Categorization of BoR will be based on RECIST using the following response categories: CR, PR, SD, PD and NE.

CR or PR must be confirmed. For determination of a best response of SD, the earliest of the dates contributing towards a particular overall visit assessment will be used. SD should be recorded at least 8 weeks minus 1 week, ie, at least 49 days (to allow for an early assessment within the assessment window), after durvalumab initiation. For CR/PR, the initial overall visit assessment that showed a response will use the latest of the dates contributing towards a particular overall visit assessment.

For patients whose progression event is death, BoR will be calculated based upon all evaluable RECIST assessments prior to death.

For patients who die with no evaluable RECIST assessments, if the death occurs  $\leq$  9 weeks (ie, 8 weeks + 1 week to allow for a late assessment within the assessment window) after durvalumab initiation, then BoR will be assigned to the progression (PD) category. For patients who die with no evaluable RECIST assessments, if the death occurs  $>$  9 weeks after Day 1 then BoR will be assigned to the NE category.

A patient will be classified as a responder if the RECIST criteria for a CR or PR are satisfied at any time following Day 1, prior to RECIST progression and prior to starting any subsequent cancer therapy.

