### **4.4.3 Objective Response Rate**

The ORR will be estimated for the SAF and will be presented with the corresponding exact 95% CIs.

The number (%) of patients with a confirmed response and the number (%) of patients with a single visit response (ie, an unconfirmed response) will also be presented.

Best objective response (BoR) will be summarised by n (%) for each category (CR, PR, SD, PD and NE).

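### Treated patients with no lesions at baseline cannot be responders but count in the ORR denominator, and best objective response has no category for them

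*SAP*

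**What the plan says.** - **Eligibility.** Protocol 5.1, criterion 9(a), covers "Patients with measurable disease and/or nonmeasurable and/or no evidence of disease assessed at baseline by computed tomography" or MRI; SAP 2.2.1 restates it. Protocol 4.1 and SAP 1.2 also allow entry in CR after radiotherapy.
- **ORR.** SAP 3.3.3 opens with "The ORR is defined for the SAF as follows" and continues: "The ORR is the proportion (%) of patients with an overall response of CR or PR", with confirmation required. SAP 4.4.3: "The ORR will be estimated for the SAF and will be presented with the corresponding exact 95% CIs". The SAF, in SAP 2.1.1, "will consist of all patients who received at least one dose (partial or in full) of durvalumab". Protocol 9.3 adds: "All analyses will be performed on the safety analysis set". Neither document defines a measurable-disease or response-evaluable set.
- **Visit response.** SAP 3.1.1.1 sets the target-lesion response to NA when there is no measurable disease at baseline. SAP Table 4 then has a separate outcome for patients with neither kind of lesion, given in its legend as "NED no evidence of disease".
- **Best response.** SAP 3.3.4: "Categorization of BoR will be based on RECIST using the following response categories: CR, PR, SD, PD and NE". SAP 4.4.3 uses the same five categories for the summary. No legible text maps NED to any of them.

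**The concern.** The SAP foresees patients with no lesions at baseline and gives them their own visit response, but drops that response one step later. This has two consequences.

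First, the planned ORR mixes two things: how often tumours that could shrink did so, and how many patients had nothing to shrink. A reader of the single figure cannot separate them.

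Second, the BoR table cannot be programmed from the text for these patients, so someone must choose a rule. The choices give different tables. Placing them under NE reports fully assessed patients as not evaluable, although the PFS rule in SAP 3.3.1 excludes only NE or missing results, so an NED scan counts as evaluable there. Treating NED as missing brings in the default non-missing denominator of SAP 4.1.1, and BoR percentages would then rest on a different base from ORR.

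**Working it through.** **Step 1: trace the rules.** Reading SAP Table 4 by baseline lesion status:

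| Baseline status | Possible visit responses | Can be CR? | Can be PR? |
|---|---|---|---|
| At least one target lesion | CR, PR, SD, PD, NE | yes | yes |
| Non-target only (target NA) | CR, SD, PD, NE | yes | no |
| Neither (NED) | NED; PD if a new lesion appears | no | no |

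All three rows are in the ORR denominator. Only the last is structurally unable to contribute to the numerator.

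**Step 2: follow an NED patient into BoR (SAP 3.3.4).**
- First assessment shows a new lesion: PD, defined.
- Death within 9 weeks with no evaluable assessment: PD, defined.
- Death after 9 weeks with no evaluable assessment: NE, defined.
- NED at every visit: no category.
- NED, then PD: undefined, because BoR is the best response up to progression and NED has no rank.

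The gap therefore concerns patients with at least one NED visit before any progression.

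**Step 3: size of the denominator effect.** Neither document states an expected ORR, so there is no plan figure to reproduce. The only precision figures concern the Grade 3/4 possibly related adverse event rate and do not bear on this point.

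Let N be the number treated, u the share with no target lesion, and c the number of confirmed CRs among non-target-only patients. Then

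ORR(SAF) = ORR(target) × (1 - u) + c/N.

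If those without target lesions are all NED, c = 0 and u = f, so the loss is ORR × f. At an assumed 30%: 0.30 × 0.05 = 1.5 points, and 0.30 × 0.30 = 9 points.

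In whole patients, with N = 102 (SAP 1.3), c = 0 and exact Clopper-Pearson 95% CIs:

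| Assumed f | Able to respond | ORR in those | ORR on SAF |
|---|---|---|---|
| 5% | 97 | 29/97 = 29.9% (21.0 to 40.0) | 29/102 = 28.4% (19.9 to 38.2) |
| 10% | 92 | 28/92 = 30.4% (21.3 to 40.9) | 28/102 = 27.5% (19.1 to 37.2) |
| 20% | 82 | 25/82 = 30.5% (20.8 to 41.6) | 25/102 = 24.5% (16.5 to 34.0) |
| 30% | 71 | 21/71 = 29.6% (19.3 to 41.6) | 21/102 = 20.6% (13.2 to 29.7) |

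If instead 20 patients have non-target disease only and 4 of them reach CR, the figures are 25/82 = 30.5% and (25 + 4)/102 = 28.4%, a gap of 2.1 points rather than 6.0.

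**Step 4: what decides who has a target lesion.** All patients have had radiotherapy. SAP 3.1.1.1 defines measurable disease so as to exclude lesions irradiated before. The note in SAP 1.1.2 and criterion 9(b), restated in SAP 2.2.1, allow irradiated lesions as target lesions if otherwise measurable. The SAP paragraph on irradiated lesions, like Protocol Appendix F, allows one only when no other lesion is available. The share u depends on which of these was applied.

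**The case against.** The strongest reply is that the all-treated denominator is a declared choice. Both documents say that efficacy uses the safety set, and ORR is a descriptive secondary endpoint in a single-arm study with no test and no target. Counting everyone dosed is a recognised conservative summary. This stands: the SAF analysis should not be replaced.

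It is also fair that part of the information is already planned. SAP 3.5.1 collects evidence of disease at entry as yes/no, SAP 4.2.3 summarises extent of disease, and target and non-target visit responses are to be listed with new-lesion status. The split into target, non-target only and NED is not explicitly tabulated, however, and no ORR on another denominator is planned.

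Three stronger readings are tempting, but the documents do not support them:
- *NED patients will be counted as NE, inflating that row.* No rule says so. Table 4 keeps NED and NE apart, and NE is reserved for other situations. It is one possible programming outcome.
- *Everyone without a target lesion is a built-in non-responder.* Table 4 gives CR to a patient with target NA and non-target CR.
- *The ORR comparison between radiotherapy cohorts is biased.* Results are summarised separately by cohort, but the legible text plans no ORR contrast, and the NED share by cohort is not given.

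The size is also uncertain. Even at f = 20%, the SAF interval (16.5 to 34.0) contains 30.5%.

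**Conclusion.** The point holds as a gap in specification and a limit on interpretation. As written, patients with no baseline lesions are ORR non-responders by construction, and those with an NED visit before any progression have no defined BoR category.

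A reader might infer that the planned ORR is wrong or that it understates activity. The documents support only a narrower statement: it is lower than the rate among patients able to respond, by the factor (1 - f), and only to the extent that NED patients are enrolled. The range of about 1.5 to 9 percentage points rests on an assumed 30% ORR, an assumed f of 5% to 30%, and no responses among the rest. It shrinks if those without target lesions include non-target-only patients who reach CR. Neither the ORR nor f is in the documents. The primary safety endpoint is unaffected. This is a low-cost improvement, not a flaw that undermines the analysis.

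**What to change.** 1. Keep ORR on the SAF as planned.
2. Add a supplementary confirmed ORR with exact 95% CI in patients with at least one target lesion at baseline, overall and by cohort.
3. Tabulate baseline status as target, non-target only, or NED.
4. Add an NED row to the BoR derivation (SAP 3.3.4) and summary (SAP 4.4.3), stating how NED followed by PD is classified.
5. Reconcile the definition of measurable disease in SAP 3.1.1.1 with SAP 1.1.2, SAP 2.2.1 and the SAP paragraph on irradiated lesions, because this decides who enters the supplementary analysis.

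The inputs are already collected, so the cost is one extra ORR row, one BoR category and a short table. The drawback is a second ORR on a smaller denominator with a wider interval: in the f = 20% illustration, 20.8 to 41.6 against 16.5 to 34.0. Label it as supplementary and specify it before database lock so that it is not a post hoc choice.

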### **3.3.4 Best Objective Response**

Best objective response (BoR) is the best response a patient has had after Day 1 up until progression, or the last evaluable assessment in the absence of progression. Responses that occur after the start of subsequent anti-cancer therapy must be excluded from the derivation. Categorization of BoR will be based on RECIST using the following response categories: CR, PR, SD, PD and NE.

CR or PR must be confirmed. For determination of a best response of SD, the earliest of the dates contributing towards a particular overall visit assessment will be used. SD should be recorded at least 8 weeks minus 1 week, ie, at least 49 days (to allow for an early assessment within the assessment window), after durvalumab initiation. For CR/PR, the initial overall visit assessment that showed a response will use the latest of the dates contributing towards a particular overall visit assessment.

For patients whose progression event is death, BoR will be calculated based upon all evaluable RECIST assessments prior to death.

For patients who die with no evaluable RECIST assessments, if the death occurs  $\leq$  9 weeks (ie, 8 weeks + 1 week to allow for a late assessment within the assessment window) after durvalumab initiation, then BoR will be assigned to the progression (PD) category. For patients who die with no evaluable RECIST assessments, if the death occurs  $>$  9 weeks after Day 1 then BoR will be assigned to the NE category.

A patient will be classified as a responder if the RECIST criteria for a CR or PR are satisfied at any time following Day 1, prior to RECIST progression and prior to starting any subsequent cancer therapy.

### **3.3.5 Duration of Response**

For patients who are classified as responders (see Section 3.3.3), the DoR is defined as the time from the date of first documented response (which is subsequently confirmed) until the first date of documented progression or death in the absence of disease progression

- DoR = (date of PFS event or censoring) – (date of start of response) +1

The date of the end of response will coincide with the date of disease progression or death from any cause used for the PFS endpoint (see Section 3.3.1). If a patient does not progress following a response, then their DoR will be censored at the date used in the PFS censoring. The date of

the initial response will be defined as the latest of the dates contributing toward the first visit response of CR or PR that was subsequently confirmed. DoR will not be defined for those patients who do not have documented confirmed response.

DoR will also be obtained using the algorithm described above for the RECIST 1.1 site Investigator tumor data

### 3.3.6 Lung Cancer Mortality

The lung cancer mortality (NSCLC-related death) is assessed using the deaths which are reported as 'NSCLC-related' and is defined as the time (days) from the date of first dose of durvalumab until date of death due to lung cancer as follows:

- Time to lung cancer mortality = (date of NSCLC-related death or censoring) – (date of first dose of durvalumab) + 1

Any patient not known to have died will be censored at the date at which the patient was last known to have been alive. Patients who died due to reasons other than NSCLC will be censored at the date of death.

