8.3.11 Deaths

All deaths that occur during the study treatment period, or within the protocol-defined follow-up period after the administration of the last dose of study drug, must be reported as follows:

- Death clearly resulting from disease progression should be reported to the Study Monitor/Physician at the next monitoring visit and should be documented in the eCRF in the Statement of Death page. It should not be reported as an SAE.
- Where death is not due (or not clearly due) to progression of the disease under study, the AE causing the death must be reported to the Study Monitor/Physician as an SAE within 24 hours. It should also be documented in the Statement of Death page in the eCRF. The report should contain a comment regarding the coinvolvement of PD, if appropriate, and should assign main and contributory causes of death.
- Deaths with an unknown cause should always be reported as an SAE. It should also be documented in the Statement of Death page in the eCRF. A postmortem may be helpful in the assessment of the cause of death, and if performed, a copy of the post-mortem results should be forwarded to AstraZeneca Patient Safety or its representative within the usual timeframes.

Deaths occurring after the protocol-defined safety follow-up period after the administration of the last dose of study drug should be documented in the Statement of Death page. If the death occurred as a result of an event that started post the defined safety follow-up period and the event

is considered to be due to a late onset toxicity to study drug then it should also be reported as an SAE.

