8 **PFS (days)** = Date of event or Censor date – treatment start date + 1

9 Patients who have not progressed or died at the time of analysis will be censored at the time of the latest date of assessment from their last evaluable assessment. However, if the patient progresses or dies after 2 or more missed visits, the patient will be censored at the time of the latest evaluable assessment prior to the 2 missed visits. If the patient has no evaluable visits or does not have baseline data, he/she will be censored at Day 1 unless he/she dies within 2 visits of baseline, in which case the date of death is the event date.

10 **OS:** Defined as the time from the first date of treatment until death due to any cause.

11 **OS (days)** = Death date or Censor date - treatment start date + 1

12 Any patient not known to have died at the time of analysis will be censored based on the last recorded date on which the patient was known to be alive.

13 Lung cancer mortality (NSCLC-related death): Defined as the time from the date of treatment start until death due to lung cancer.

Time to NSCLC-related deaths (days) = NSCLC-related death date or Censor date - treatment start date + 1

Any patient not known to have died due to lung cancer will be censored based on the last recorded date on which the patient was known to be alive or died due to reason other than lung cancer.

14 **ORR:** Based on Investigator-assessed response to treatment of CR and PR, per RECIST1.1.

15 **DoR:** Defined as the time from the date of first documented response per RECIST1.1 until the first date of documented progression per RECIST1.1 or death in the absence of disease progression.

- 16 DoR (days) = Date of PFS event or censoring – Date of first response + 1
- 17 The end of response should coincide with the date of progression or death from any cause used for the PFS endpoint. If a patient does not progress following a response, then the patients' DoR will be censored at the PFS censoring time. DoR will not be defined for those patients who do not have a documented response.

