#### **4.4.5 Time to Lung Cancer Mortality (NSCLC-Related Death)**

The following numbers (%) of patients in the SAF will be presented at 12-monthly intervals and overall: those with an NSCLC-related death, those still in survival follow-up, those lost to follow-up, those who withdrew consent, and those with censored time to lung-cancer mortality (separately for those who died from a cause not related to NSCLC and other reasons for censoring, as well as overall).

Kaplan-Meier plots and descriptive statistics will be presented for time to NSCLC-related mortality. Summaries will include the lower and upper quartile and median lung cancer mortality and estimates at Month12 (Day 365).

All summary statistics will be presented with the appropriate 95% CI.

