  - This summary will include an AE event rate (per 100 patient years) for each PT. The number of patients with an AE in each PT is divided by the sum of the actual exposure to durvalumab (days) (see Section 0) over all patients. This is multiplied by 365.25 x 100 to create an event rate per 100 patient years.
- All AEs by maximum CTCAE Grade
- All AEs / PRAEs with outcome of death
- All SAEs / Serious PRAEs
- All AEs / PRAEs leading to discontinuation from durvalumab (Note: Reason for discontinuation recorded on the patient disposition page)
- All AEs / PRAEs leading to dose interruption/discontinuation of durvalumab (Note: Reason for discontinuation recorded on the patient disposition page)

A summary of most common AEs and another summary of most common AEs with CTCAE Grade 3 or higher, including all events that occur in at least 2.5% of patients overall will be presented by PT, by decreasing frequency. This cut-off may be modified after review of the data. The raw percentage will be compared to the cut-off, without applying any rounding to the percentage value (ie, a TEAE with frequency of 2.4% will not appear in the table if a cut-off is 2.5%).

A summary of deaths will be provided with the following information:

- Number of deaths (NSCLC-related, non-related, and unknown)
  - Number of deaths during the on-treatment study period up until 90-day follow-up

- and prior to initiation of first subsequent therapy
- Number of deaths occurring more than 90 days after the discontinuation of durvalumab or after initiation of first subsequent therapy

Listings of key patient information for Deaths and SAEs will be provided.

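### Lung cancer mortality is estimated by Kaplan-Meier with other-cause deaths censored; given the recorded causes this overstates cumulative NSCLC mortality and tends to bring the median too early, by an amount the documents do not let us fix

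*SAP*

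**What the plan says.** SAP 3.3.6 counts as events only deaths reported as NSCLC-related. Its formula runs from first dose to that death or to censoring, and it gives two censoring rules: "Any patient not known to have died will be censored at the date at which the patient was last known to have been alive", and "Patients who died due to reasons other than NSCLC will be censored at the date of death".

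Protocol 9.4 uses one broader rule: "Any patient not known to have died due to lung cancer will be censored based on the last recorded date", meaning either the last date alive or the date of a death from another cause.

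SAP 4.4.5 plots this variable by Kaplan-Meier and summarises it by both quartiles, the median and a Day 365 value, with 95% CIs. Protocol 9.5.2.2 and the synopsis give a Kaplan-Meier median with 95% CI. SAP 4.4.5 also tabulates, at 12-monthly intervals and overall, NSCLC deaths and censored patients, the latter "separately for those who died from a cause not related to NSCLC and other reasons for censoring, as well as overall".

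Unknown causes are foreseen. The deaths summary in SAP 4.5.1 has a separate unknown category, and Protocol 8.3.11 states: "Deaths with an unknown cause should always be reported as an SAE".

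No readable part of either document mentions competing risks, plans a cumulative incidence estimate, or declares a hypothetical (net) mortality as the target.

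**The concern.** A patient who has died of another cause can no longer die of lung cancer. Censoring that patient in a Kaplan-Meier analysis treats the future risk as still open. The result answers what NSCLC mortality would be if nobody died of anything else and the causes were independent. The plan labels it simply as lung cancer mortality.

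The issue is relevant here because patients are unfit for chemotherapy through comorbidity, poor performance status or age (Protocol 2), and performance status 2 is allowed. Some non-cancer deaths must be expected.

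At stake is one named but descriptive secondary efficacy endpoint. Its main protocol statistic, the median, could come out too early, or be reported when cumulative NSCLC mortality never reaches 50%. The primary endpoint, PFS and OS are unaffected.

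**Working it through.** The plan gives no planning figure for this endpoint, so there is nothing of its own to reproduce.

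**Direction.** At each NSCLC death the Aalen-Johansen estimate rises by (all-cause survival just before) × d/n, where d is NSCLC deaths and n the number at risk. 1-KM rises by (NSCLC-only Kaplan-Meier just before) × d/n. The second multiplier is never smaller than the first, and is larger once an other-cause death has occurred. So 1-KM is never below the cumulative incidence, and exceeds it once an NSCLC death follows an other-cause death. In 4,000 simulated trials (n=102, median OS 18 months, 30% other-cause deaths, censoring uniform over 18-48 months) there was no exception. The KM median was never later, and it was strictly earlier in 99.5%.

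**Inputs.** From the documents: about 102 treated patients, 43 of them in the palliative cohort (Protocol 9.2); 12-month OS of 83.1% with durvalumab in PACIFIC (Protocol 2.3.1). Assumed: constant hazards, 12-month OS of 50-75% as a less fit alternative, other-cause share of deaths s = 10-50%.

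**Formulas.** h = -ln(OS12)/12 and f = 1 - s.
- 1-KM(t) = 1 - exp(-f·h·t)
- Cumulative incidence CIF(t) = f·(1 - exp(-h·t))
- KM median = ln 2/(f·h)
- CIF median = -ln(1 - 0.5/f)/h if f > 0.5, otherwise never reached

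**Results.** The 63% rows use h = ln 2/18, a median OS of 18 months. Gaps come from unrounded values.

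| 12-month OS | Other-cause share | Month 12: 1-KM / CIF (gap) | Month 24: 1-KM / CIF (gap) | Median, months: KM / CIF |
|---|---|---|---|---|
| 83.1% | 10% | 15.3 / 15.2 (0.1) | 28.3 / 27.8 (0.5) | 49.9 / 52.6 |
| 83.1% | 50% | 8.8 / 8.5 (0.4) | 16.9 / 15.5 (1.4) | 89.9 / never |
| 75% | 10% | 22.8 / 22.5 (0.3) | 40.4 / 39.4 (1.0) | 32.1 / 33.8 |
| 63% | 20% | 30.9 / 29.6 (1.3) | 52.3 / 48.3 (4.0) | 22.5 / 25.5 |
| 63% | 30% | 27.6 / 25.9 (1.7) | 47.6 / 42.2 (5.4) | 25.7 / 32.5 |
| 63% | 50% | 20.6 / 18.5 (2.1) | 37.0 / 30.2 (6.8) | 36.0 / never |
| 50% | 50% | 29.3 / 25.0 (4.3) | 50.0 / 37.5 (12.5) | 24.0 / never |

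**Against sampling error.** For a 22% risk, 1.96·√(0.22·0.78/n) is about 8 points at n=102 and 12 at n=43. Every Month-12 gap is smaller.

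For the median, trials of n=102 were simulated with follow-up assumed at 18-36 months and the log-log Brookmeyer-Crowley interval. At OS 63%, the KM interval contained the CIF median in 94, 86, 77 and 89% of trials reporting a median, at shares of 10, 20, 30 and 40%. Its upper limit was not reached in 14, 43, 72 and 89%. At OS 50% the coverage figures were 93, 85, 67 and 38%. A KM median with no CIF median arose in 0, 7, 34, 49 and 36% of trials at OS 63% (shares 10-50%), and in 4-15% at OS 75%.

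**Unknown causes.** Take OS 63% and 30% other-cause among known causes, with unknown-cause deaths censored, at Month 24. If 10% of deaths are unknown, the recorded NSCLC fraction is 0.9 × 0.7 = 0.63 and 1-KM is 44.1%. If all those unknowns were truly NSCLC, actual NSCLC mortality is (0.63 + 0.10) × 0.603 = 44.0%. If 20% are unknown, the fraction is 0.56, 1-KM is 40.4%, and actual mortality is 0.76 × 0.603 = 45.8%. The upward bias disappears in the first case and reverses in the second.

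**The case against.** Four arguments can be made for leaving the plan alone.

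- Censoring other-cause deaths gives a recognised net summary, and the endpoint is descriptive, with no test, comparator or decision rule. This limits the gravity. It does not excuse the label, because the plan never states a net target or the independence it needs.
- The 12-monthly counts in SAP 4.4.5 show NSCLC and other-cause deaths, and all-cause OS is reported in full. At the final analysis (SAP 5) those counts nearly give the Month-12 cumulative incidence, apart from early losses and without a CI. They do not correct the curve, quartiles or median.
- The effect may be trivial. At the only durvalumab survival figure in the documents it is, and a median is unlikely to be reached. That population was fitter, so the figure is an anchor rather than a forecast.
- A reader might infer that the SAP has no rule at all for unknown-cause deaths, so that results move with how they are coded. The documents do not support that. Only deaths reported as NSCLC-related are events, and the formula allows only such a death or censoring; Protocol 9.4 censors anyone not known to have died of lung cancer. At OS 63%, 20% other-cause and 10% unknown, the Month-12 cumulative incidence is 25.9% with unknowns as competing and 29.6% with unknowns as NSCLC. That contrast shows sensitivity to misclassified causes, since both documents exclude the second coding. What remains open is the censoring date (death or last known alive) and the missing sensitivity analysis.

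**Conclusion.** The point holds. Given the recorded causes, the planned Kaplan-Meier output overstates cumulative NSCLC mortality once an NSCLC death follows an other-cause death, and its median is never later and usually earlier than the cumulative incidence median.

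The size depends on survival and on the other-cause share, neither of which the documents give for this population. It is 0.1-0.4 points at Month 12 and 0.5-1.4 at Month 24 at a 12-month OS of 83.1%, and 0.3-4.3 and 1.0-12.5 points at an assumed OS of 50-75%. Month-12 effects are within sampling error, and at shares of 10-20% the median shift usually lies inside the CI. Material harm needs both poor survival and a share of about 30% or more.

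A reader might infer that true NSCLC mortality will certainly be overstated. That goes too far: the direction is fixed only for the causes as recorded, and censored unknown-cause deaths that were truly NSCLC can shrink or reverse the net bias.

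**What to change.** Amend SAP 3.3.6 and 4.4.5, add an entry to SAP section 6, and align the protocol (synopsis, 9.4, 9.5.2.2) at its next amendment:

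- Make the Aalen-Johansen cumulative incidence of NSCLC-related death, with other-cause death as a competing event, the estimate of lung cancer mortality. Report Month 12 with 95% CI, overall and by cohort, and a median only if cumulative incidence reaches 50%.
- Keep the Kaplan-Meier output only as a supplement, labelled as a net estimate that assumes independent causes.
- Add one sentence saying how unknown-cause deaths are classed in the main analysis, and one sensitivity analysis counting them first as NSCLC-related and then as competing.

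No new data are needed: dates of death and the three-way cause split are already planned. The cost is a little extra output and a departure from the protocol-stated Kaplan-Meier method on a descriptive secondary endpoint.
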